## 1 PURPOSE

This Statistical Analysis Plan (SAP) has been designed to document the rationale for the study design, and the planned analyses that will be included in study reports.

## 2 RATIONALE FOR STUDY DESIGN

### 2.1 Study Purpose

The pivotal trial (STOP -AF) of the Arctic Front® Cardiac Cryoablation Catheter System with the adjunctive use of the Freezor® MAX Cardiac Cryoablation Catheter to electrically isolate pulmonary veins (PV) in patients with paroxysmal atrial fibrillation (PAF), compared to a randomized drug control group has been performed and a final report submitted to the FDA resulting in product approval December 2010. A Continued Access Protocol trial (CAPAF) was also conducted to allow collection of additional safety data following modifications implemented into the Arctic Front® Catheter and Cryoablation System. As part of the continued clinical development of the Arctic Front® Cardiac Cryoablation Catheter System, this Post Approval Study (PAS) is being conducted to provide long-term safety and effectiveness monitoring/data per the Pre-Market Approval order (P100010) by the Food and Drug Administration (FDA).

This PAS is a prospective multicenter, non-randomized, single arm, controlled, unblinded clinical study of up to 400 enrolled subjects with PAF who have failed one or more Atrial Fibrillation Drugs (AFDs). All study subjects will be receiving cryoablation with the study devices and, optionally (post-procedure), an Atrial Fibrillation Drug.

### 2.2 Study Scope

The study is expected to enroll subjects over an 18 - 24 month period with post procedural follow-up consisting of clinic visits at 6 and 12 months, and 2 and 3 years. There was a CIP change in June of 2016 that reduced the follow up time of this study from 5 years to 3 years. Prior to sites' activation of version 6 of the CRF, some subjects may also have been seen at 4 year or 5 year visits. This data will be included in the summary of safety outcomes.

Since the primary endpoint of the study is assessed at 3 years, the power of the study is not affected by this change.

More than 30 investigational sites in the United States and Canada have participated in this investigation. The Principal Investigator is [name] at Northwestern Memorial Hospital in Chicago, Illinois.

## 2.3 System Description

The investigational devices to be used in this trial are formally defined in the STOP AF PAS CIP version 6 (30JUN2016) Section 3. These devices include:

[figure not shown]
Arctic Front® Cardiac CryoAblation System, consisting of:

- Arctic Front® Cardiac CryoAblation Catheter OR
- Arctic Front Advance™ Cardiac CryoAblation Catheter
- Manual Retraction Kit
- The Freezor® MAX Cardiac CryoAblation Catheter
- Medtronic CryoCath CryoConsole

## 2.4 Data Collection

Clinical data are required to be collected at baseline/enrollment, procedure, post procedure, discharge, month (3, 6) followup, and year (1, 2, 3) followup. If a subject exits early, then a termination visit will also be conducted. The overall study design is summarized in Figure 1.

Figure 1: STOP AF PAS Overall Study Design

This SAP is based on Version 6 of the STOP AF PAS Clinical Investigation Plan (30JUN2016).

### 3 DESCRIPTION OF ANALYSIS

#### 3.1 General Summaries

##### 3.1.1 Analysis Sets

**Enrolled Set:** any subjects who have a signed informed consent.

**Intent-To-Treat Set (ITT):** any enrolled subjects who meet all inclusion and exclusion criteria.

**mITT (modified intent-to-treat) Set:** any subjects within the ITT set with an Arctic Front® Cardiac CryoAblation Catheter System inserted into the vasculature for the purpose of this study.

**All Treated Set:** any subjects who have signed informed consent and have an Arctic Front® Cardiac CryoAblation Catheter System inserted into the vasculature.

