## 3.2 Primary Objectives

The study will be considered a success if both primary effectiveness and safety objectives are met at one-sided 0.025 level of significance in the final analysis. The analysis will be conducted using all mITT subjects.

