### 3.2.2.2 Endpoint Definition

A CPE is a device-related or procedure-related serious adverse event (SAE) with onset between the time of the subject's entry into the procedure room for the study-specified cryoablation procedure (Day 0) through the indicated onset intervals as set out in the following Table 1:

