#### B. Determination of Subject s/Data for Analysis

The analysis will be conducted using the modified intent-to-treat (mITT) set.

[figure not shown]

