### 3.2.2.4 Sample Size Methods and Assumptions

Sample size was estimated using SAS v9.2 Proc Power. The sample size was calculated under an asymptotic z-test for a single binomial proportion with a continuity adjustment under the following assumptions:  
Power = 90%, Significance level = 0.025 (one-sided), Assumed underlying primary safety event rate = 6%, Performance goal = 14.8%.

The performance goal of 14.8% is selected based on the same assumption defined in version 1.7 of the STOP AF Clinical Investigation plan (January, 2008): "Based on a review of SSEDs for similar types of ablation trials, the expected rate for CPEs in a well-monitored trial of left atrial RF ablation for AF was estimated to be 10% (corresponding to a CPE-free rate of 90%). If 16 of 160 subjects were observed to have at least one CPEs then the resulting one-sided 95% upper confidence bound would be 14.8%."; where SSED is an abbreviation for Summary of Safety and Effectiveness Data.

Figure 3 presents the sample size at different primary safety event rates under the assumptions outlined above.

Figure 3. Sample Size vs. Primary Safety Event Rate

If the underlying safety event rate is assumed 6%, a total of 141 evaluable/mITT subjects will be required to provide 90% power to meet this safety objective.

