#### 3.3.6.3 Analysis Methods

##### A. Statistical Methodology

All adverse events will be summarized by presenting the number of events, the number and percentage of subjects having any AE, having an AE in each body system, and having each individual AE. Any other information collected (e.g., seriousness, severity or relatedness to device/procedure) will be presented as appropriate.

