##### B. Determination of Subjects/Data for Analysis

The population used for descriptive statistics will be the enrolled set. Summaries will be presented for both the Intent-To-Treat (ITT) Set and Modified Intent-To-Treat (mITT) Set.

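### Primary safety: a CPE in a subject who enters the procedure room but never has the catheter inserted meets the endpoint, yet enters no planned CPE rate

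*SAP*

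**What the plan says.** **Endpoint window.** SAP 3.2.2.2 defines a CPE as a serious adverse event related to the device or the procedure, "with onset between the time of the subject's entry into the procedure room for the study-specified cryoablation procedure (Day 0"), running through the intervals in Table 1.

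**Primary set.** SAP 3.2 says of both primary objectives: "The analysis will be conducted using all mITT subjects". Section 3.2.2.3 B repeats this for safety: "The analysis will be conducted using the modified intent-to-treat (mITT) set". By 3.1.1, mITT means "any subjects within the ITT set with an Arctic Front® Cardiac CryoAblation Catheter System inserted into the vasculature for the purpose of this study".

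**Alternative set.** The All Treated set (3.1.1) is "any subjects who have signed informed consent and have an Arctic Front® Cardiac CryoAblation Catheter System inserted into the vasculature". It drops the eligibility condition but keeps insertion. Section 4.4 leaves a repeat on this set to discretion, and its stated aim is sensitivity to the inclusion and exclusion criteria.

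**Wider reporting.** For the general adverse event summary, 3.3.6.3 B states: "The population used for descriptive statistics will be the enrolled set", and adds ITT and mITT presentations. Section 3.3.6.3 A gives "the number and percentage of subjects having any AE, having an AE in each body system, and having each individual AE", with seriousness, severity and relatedness shown as appropriate. Section 3.1.2 bases seriousness and relatedness on the adjudication committee's determination. Section 3.1.3 summarises disposition, including allocation to analysis sets.

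**The concern.** The endpoint clock starts at room entry, while the set on which the rate is estimated starts at catheter insertion. A serious procedure-related event between the two can end the procedure. Membership of the safety denominator then depends on the safety outcome, because the event removes its own subject.

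The interval is not empty by the SAP's own account. Section 3.3.5.2 times the procedure from skin puncture for venous access, and Table 1 includes access site complications, arrhythmias and death.

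The trial is single-arm and is judged against a fixed 14.8% goal, so no control group is subject to the same exclusion. At stake is whether the reported CPE rate covers the window that the endpoint defines.

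A second, separate gap concerns treated subjects who prove ineligible. They are outside mITT, and whether a CPE rate ever includes them is left to a later judgement.

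**Working it through.** **1. Which planned analysis would include the event?** Take a consented subject who enters the room, has a procedure-related CPE and is never inserted.

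| Analysis (SAP section) | Set | Subject included? |
|---|---|---|
| Primary CPE rate (3.2, 3.2.2.3 B) | mITT | No |
| Tipping-point or worst-case analysis (3.1.4.2) | mITT | No |
| Discretionary repeat (4.4) | All Treated | No |
| MAFE (3.3.2) | mITT; events categorised as CPEs excluded | No |
| Long-term safety (3.3.3) | mITT | No |
| General adverse events (3.3.6) | enrolled named; ITT and mITT presented | Yes, as an adverse event |
| Disposition (3.1.3) | set allocation | Yes, as a subject |

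If the catheter is inserted after the event, the subject is in mITT and the event counts, since follow-up runs from Day 0 (3.2.2.3 A).

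**2. The plan's own safety sample size.** Inputs from 3.2.2.4: p0 = 0.148, p1 = 0.06, one-sided alpha 0.025, power 90%, z-test with continuity adjustment.

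n = [(1.960·√(0.148·0.852) + 1.282·√(0.06·0.94)) / 0.088]² = [(0.6960 + 0.3044)/0.088]² = 129.2.

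With continuity adjustment: (129.2/4)·[1 + √(1 + 2/(129.2·0.088))]² = 140.4, so 141. This agrees with the SAP; no stated figure is disputed.

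**3. Size of the effect.** The SAP does not say how many subjects enter the room without insertion. Call this m. Section 4.1 plans up to 400 enrolled and 370 mITT, so I assume m between 0 and 400 − 370 = 30. Let k be the CPEs among them. With no censoring before 12 months, the log-log upper limit for x events in n subjects is

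S = 1 − x/n; v = √(x/(n(n − x))) / |ln S|; upper = 1 − S^exp(1.96·v).

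Planned rate: 6% of 370 is 22.2, so x = 22. S = 0.9405, v = 0.01307/0.06130 = 0.2132, exp(1.96·0.2132) = 1.519, upper = 8.89%.

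| Starting point | Added (k of m) | Rate | Upper limit | 14.8% goal |
|---|---|---|---|---|
| 22/370 | none | 5.95% | 8.89% | met |
| 22/370 | 1 of 5 | 23/375 = 6.13% | 9.09% | met |
| 22/370 | 1 of 30 | 23/400 = 5.75% | 8.53% | met |
| 22/370 | 5 of 30 | 27/400 = 6.75% | 9.69% | met |
| 22/370 | 22 of 22 | 44/392 = 11.22% | 14.79% | met |
| 22/370 | 23 of 23 | 45/393 = 11.45% | 15.03% | not met |
| 22/370 | 24 of 30 | 46/400 = 11.50% | 15.05% | not met |
| 41/370 | none | 11.08% | 14.75% | met |
| 41/370 | 1 of 1 | 42/371 = 11.32% | 15.01% | not met |
| 41/370 | 1 of 10 | 42/380 = 11.05% | 14.66% | met |

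41 events is the most that 370 subjects can have and still pass. An intermediate case is an observed 10% (37/370). This is the historical figure in 3.2.2.4, where "the expected rate for CPEs in a well-monitored trial of left atrial RF ablation for AF was estimated to be 10" per cent; it is not this plan's 6% assumption. Reversal there would take from 5 of 5 (42/375, 14.85%) to 9 of 30 (46/400, 15.05%).

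**4. Dependence on censoring.** Suppose instead that event-free non-inserted subjects are censored before any mITT event occurs. Then m = 30, k = 1 gives 1 − (399/400)(348/370) = 6.18%, upper limit 9.16%, against 5.75% without censoring. Whether the supportive rate lies above or below the mITT rate therefore depends on m, k and follow-up. No value of m can be named at which it crosses.

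**The case against.** The strongest case for the plan is that it chooses an insertion-based set consistently, in 3.2, 3.2.2.3 B, 3.2.2.4 and 4.1. That is a reasonable denominator for a device performance goal. Section 4.1 treats mITT subjects as those with procedure attempts and the other enrolled subjects as having no procedure, so nothing in the SAP shows that m exceeds zero. The event would not be hidden either: adverse event summaries with adjudicated seriousness and relatedness, together with disposition, would show an eligible non-inserted subject as a difference between ITT and mITT.

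Much of this stands, and it is why mITT should remain primary. What it does not supply is a CPE rate with an interval over the endpoint's own window.

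A reader might infer more than the documents support:

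- *That every CPE before insertion is lost.* It is not; a subject inserted afterwards is in mITT and counted.
- *That the event goes unreported.* The general adverse event summary and disposition capture it.
- *That the mITT rate must be too favourable.* Event-free room entrants are left out as well, so the direction of the net effect is unknown.

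**Conclusion.** The point holds as a minor one. The endpoint window and every set on which a CPE rate is planned start at different moments. A CPE in a subject never inserted is lost from numerator and denominator, and that exclusion can depend on the safety event itself.

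A reader might take this to put the 14.8% conclusion in doubt. The figures do not support that: at the planned rate the conclusion reverses only with 23 or more omitted CPEs, and only near the pass boundary could a single event decide it. This rests on an assumed 0 to 30 non-inserted room entrants and, for the tabulated figures, on no censoring before 12 months. The discretionary inclusion of treated but ineligible subjects is a separate gap, also small, since 4.4 expects such subjects to be rare.

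**What to change.** Keep mITT as the primary safety set and make two separate changes.

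1. In 3.2.2.3 B and 4.4, require a supportive analysis: the 12-month Kaplan-Meier CPE rate with its two-sided 95% log-log confidence interval on all consented subjects who enter the procedure room for the study cryoablation, whether or not the catheter is inserted. Day 0 is the day of room entry, and non-inserted subjects without a CPE are censored at last contact. Report it beside the mITT result, with the number of non-inserted subjects and their CPEs.
2. In 4.4, make the All Treated repeat of the primary safety analysis mandatory. Reporting it separately keeps the effect of eligibility distinct from that of insertion.

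Cost: SAP text in two sections, two extra Kaplan-Meier runs, and committee adjudication and last-contact dates for a few subjects; the SAP does not say whether these data already exist. The supportive rate may be slightly less favourable. The primary set, hypothesis and sample size do not change.

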##### 3.1.2 Use of Adjudicated Data

For endpoint events that are to be adjudicated, only data fully adjudicated by the Adverse Event Adjudication Committee (AEAC) will be used in summaries and analyses. AEAC determination of Chronic Treatment Failure (CTF), Cryoablation Procedure Events (CPE), and Major Atrial Fibrillation Event (MAFE), and their respective onset dates, are what the endpoint analyses utilizing these events will be based on. For adverse events (AE) reporting, AEAC determination of seriousness, and relatedness status will be used. Note that for data freezes and analyses before the final report, it may not be possible for all data used to be adjudicated.

##### 3.1.3 Description of Baseline Variables

The following baseline disposition and procedural parameters reported on the case report forms (CRF) will be analyzed descriptively.

- The baseline and demographic characteristics, including but not limited to age, gender, race, height, weight, body mass index, relevant medical history, arrhythmic symptoms, comorbid conditions, cardiovascular medical history, and concomitant medications. The baseline demographic tables will be reported for both the Intent-To-Treat (ITT) Set and Modified Intent-To-Treat (mITT) Set.
- Subject disposition (analysis set allocation, discontinued along with primary reason for discontinuation, etc.) will be summarized using frequency and percent. A summary of subjects enrolled by site will be provided.

- A summary of Cryoablation procedure information including Cryoablation parameters (number, duration, average temperature, etc.), cryocatheter insertion time, PV ablation time, and total fluoroscopy time will be summarized based on the modified intent-to-treat (mITT) set

Tables and descriptive statistics will be used to summarize subject data with respect to these variables. For quantitative variables, number of nonmissing observations, mean, median, minimum, maximum and standard deviation will be calculated. For qualitative variables, percentages and counts will be calculated.

### 3.1.4 Special Considerations

#### 3.1.4.1 Pooling of Study Centers for Analysis

A study center is defined as a treatment administration site or group of treatment administrative sites under the control and supervision of the same Principal Investigator. Each study center will be limited to enrolling no more than 50 subjects into the mITT set. Each center will be encouraged to enroll at least 10 subjects into the mITT. Steps will prevent any single center from contributing a significant proportion of the subjects to the study. While every effort will be made to acquire similar enrollment from all participating centers, it is likely that some centers may enroll small numbers of subjects. Therefore (for assessment of heterogeneity only) the centers that contribute five or fewer subjects to the mITT dataset will be pooled into a single 'super center'. The participating centers with more than five subjects in the mITT dataset will be reported individually.

Assessments of heterogeneity will be performed for the primary effectiveness and safety objectives across the investigational study centers. Analysis of heterogeneity in primary endpoints will be conducted only in the final report.

The level of heterogeneity of pre-specified primary endpoints will be conducted using a random-effects meta-analytic approach. The R statistical software platform will be used to evaluate whether sites exhibit significant heterogeneity in event rates. If a Cochran's Q test for heterogeneity shows  $p < 0.15$ , it will be taken as evidence of heterogeneity between sites. Evidence of between-site heterogeneity will not preclude pooling data; rather, it may result in further investigation into the sources of the apparent differences in event rates between sites. In addition, a graphical display (such as a forest plot) of the proportions of primary effectiveness events and primary safety events along with 95% confidence intervals for each center may be constructed.

#### 3.1.4.2 Missing Data

The impact of missing data on the analysis of primary effectiveness and safety objectives is expected to be small since the Kaplan-Meier method will be performed for the primary objectives. For subjects who are lost to follow-up, the time to event will be censored at the last contact date.

Analysis will be based on available cases. The reasons for study withdrawal will be documented. There are no plans for imputation of any missing data. However, we will compare differences in baseline characteristics between subjects with complete data and subjects with early exit. Also, if the primary objectives are met ( $p < 0.05$ ) at 3 years, with >

5 subjects exiting prior to the 3-year follow-up, a tipping point analysis will be conducted to assess sensitivity to missing data. Missing data is defined here as subjects with less than 3 years of followup.

Data will be sorted by ascending event times, and subjects who are censored prior to the 3-year visit are assigned an event time equal to the date of last contact (index ablation date). Then, for each observation:

- 1) If the observation is censored, set time = time + 1 and event = 1.
- 2) Apply the logrank test (specified in section 3.2.1 or 3.2.2 for efficacy and safety, respectively) to find the new two-sided p-value and 95% loglog confidence interval.

The first observation where the confidence interval includes the performance goal (and the corresponding p-value  $\geq 0.05$ ) is the tipping point for the primary safety analysis. For either primary endpoint, if fewer than 5 subjects have missing data, a worst case analysis will be done instead of a tipping point analysis. This analysis will be performed in the mITT dataset.

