### 3.2.1.3 Analysis Methods

#### A. Statistical Methodology

The Kaplan-Meier method will be used to estimate the probability of chronic treatment success at 36 months followup. The standard error will be approximated using Greenwood's formula. A two-sided 95% log-log confidence interval for the probability will be constructed. The Kaplan-Meier estimate and its 95% log-log confidence interval will be constructed from the day of protocol specified ablation procedure (Day 0) through the end of followup. For subjects with a treatment failure, the days of followup will be computed as the days from Day 0 to the failure date. For subjects without failure events, days of followup will be computed as the days from Day 0 through the last followup. For subjects who are lost to followup, the last contact date will be used as the last followup date.

The survival curve will be presented through 36 months. Note that the phrases 'at 36 months' and 'through 36 months as used throughout includes events from the 3 year visit, even when it occurs more than  $3 \times 365 = 1,095$  days from the start date. The 36 month visit may occur after 1,095 days since the visit window runs until 30 days past day 1,095. Rhythm monitoring that was initiated at the 36 month visit will be included in the analysis of the 36 month endpoint provided that the date of the documentation is no later than 30 days after the 36 month visit. Therefore, depending on the date of the 3 year visit, it is possible to include documentation as late as day 1,155. Not including such events after day 1,095 could underestimate the proportion at 3 years due to 36 month visits that occur after 1,095 days. This potential bias is addressed in the statistical analysis by considering the date of recurrence to be exactly 36 months from the study ablation procedure so that these events will be counted as CTF in the 36 month Kaplan-Meier analysis.

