### 4.3 Interim Subject Safety Monitoring

No formal interim analyses are planned. However, accumulating data for the safety endpoints may be analyzed at any time per regulatory agency's request. Hypothesis statistical testing will not be conducted until the final analysis. No alpha adjustment will be applied in terms of the analysis of the final primary endpoint for all subjects.

Note that incidence rate estimates from analyses for the interim reports may have some upward bias since subjects that recently had a 36-month visit that occurred prior to precisely 36 months will not be part of the risk set (denominator) at 36 months due to being censored at their last followup.

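### SAP 3.1.4.2 describes the missing group in three unreconciled ways, and its formal time-based definition lets the tipping-point analysis convert observed 36-month successes

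*SAP*

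**What the plan says.** SAP 3.1.4.2 identifies the missing group in three ways.

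- **By exit (trigger).** The analysis is run when the objectives are met with more than "5 subjects exiting prior to the 3-year follow-up, a tipping point analysis will be conducted".
- **By visit (time assignment).** "subjects who are censored prior to the 3-year visit are assigned an event time equal to the date of last contact".
- **By elapsed time (formal definition).** "Missing data is defined here as subjects with less than 3 years of followup".

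The procedure then reads: "Data will be sorted by ascending event times", and for each one, "If the observation is censored, set time = time + 1 and event = 1". The tipping point is the first observation at which the interval takes in the performance goal. A second branch depends on the count of missing subjects: "if fewer than 5 subjects have missing data, a worst case analysis will be done instead of a tipping point analysis".

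Two other places bear on this. Section 3.2.1.3 sets the time at risk: "For subjects without failure events, days of followup will be computed as the days from Day 0 through the last followup". It also dates failures found after day 1,095 back to exactly 36 months. Section 4.3, writing about interim reports, acknowledges "subjects that recently had a 36-month visit that occurred prior to precisely 36 months" and says that these subjects are censored at their last follow-up.

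**The concern.** Take a subject seen CTF-free at a 36-month visit on day 1,080 and not followed further. No visit was missed and the 36-month outcome is known. By 3.2.1.3 the subject is censored at day 1,080. By the formal definition the subject has under 3 years of follow-up and is missing. By step 1 the subject may become a failure at day 1,081. Under the exit-based or visit-based wording the same subject is not missing at all.

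Two programmers could each follow the section faithfully and report different missing counts and different tipping points. The count also selects between the tipping-point and worst-case branches. At stake is the meaning of the robustness statement: a tipping point should say how many unknown outcomes must go badly, not how many known successes must be overwritten. Section 3.2.1.3 carries late failures back to 36 months but has no matching rule that carries early event-free visits forward.

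**Working it through.** **The plan's own figures.** The SAP gives no figure for the tipping-point rule, so the sample size was reproduced first. With p0 = 0.45, p1 = 0.55, one-sided alpha 0.025 and 90% power (3.2.1.4):

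- n = [(1.960·√(0.45·0.55) + 1.282·√(0.55·0.45))/0.10]², which rounds up to 261.
- With continuity correction, (n/4)·(1 + √(1 + 2/(n·0.10)))², it is 270, as stated.
- 270/0.9³ = 370.4, against the stated 370 mITT (4.1).

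**How few conversions matter.** Treat 270 evaluable subjects as a simple proportion. The log-log lower bound is exp{−exp[ln(−ln S) + 1.96·se]}, with se = √((1−S)/(S·n))/|ln S|.

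- At S = 0.55 (148.5 successes) the lower bound is 48.9%.
- The smallest number of successes with a bound above 45% is 139 (bound 45.4%). Since 148.5 − 139 = 9.5, about ten overwritten successes are enough to lose the goal.
- Overwriting 10% of successes (14.85) gives S = 49.5% and a bound of 43.4%.

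**Simulation of the rule.** From the SAP: 370 subjects, 45% goal, Kaplan-Meier with Greenwood error and log-log interval at day 1,095, late failures dated back to day 1,095, 7% annual recurrence after year 1, and the 30-day late edge of the window. Assumed: an early edge of 30 days; 25%, 50% or 75% of visits before day 1,095; follow-up ending at the visit; and the attrition and freedom rates other than 10% and 55%. There were 20 runs per setting, and only runs that first met the goal were kept (17 to 20). Ranges are over the three early-visit shares.

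| Attrition per year | Freedom at 36 months | CTF-free exits | Early completers added | Tips, exits only | Tips, literal rule | Literal tip falls on a completer |
|---|---|---|---|---|---|---|
| 10% | 55% | 67 | 37–113 | 100% | 100% | 0% |
| 10% | 65% | 74 | 44–132 | 80–85% | 100% | 15–20% |
| 5% | 55% | 34 | 43–132 | 83–89% | 100% | 11–17% |
| 5% | 65% | 38 | 51–155 | 0–5% | 100% | 95–100% |
| 2% | 55% | 13 | 48–145 | 17–22% | 100% | 78–83% |
| 1% | 55% | 7 | 49–148 | 6–11% | 100% | 89–94% |

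A repeat with 40 runs per setting put the tip on a completer in:

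- 0 of 36 successful runs at 10% per year and 55%;
- 6 of 40 at 10% and 65%;
- 24 of 40 at 10% and 70%;
- 38 of 40 at 5% and 65%, whether the early edge was 30 or 7 days.

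The first row shows no effect because early completers sort last: with about 67 exits ahead of them, the bound has crossed 45% before any is reached. The exits-only column leaves early completers censored at their visit. It therefore isolates the choice of definition and does not include carrying them to 36 months.

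**The case against.** The strongest defence is that the section, read as a whole, means early exit. The trigger speaks of exiting, the time assignment refers to the visit, the planned baseline comparison is between complete data and early exit, and 3.2.1.3 ties the 36-month endpoint to the 3-year visit and not strictly to day 1,095. This stands to the extent that the fault is an unreconciled definition and not one clear wrong rule. It does not settle the matter, because the only sentence that defines missing data is the time-based one and step 1 exempts nobody.

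Three further points stand.

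- The note in 4.3 concerns interim reports. It shows that early visits occur, not how many subjects stay censored before day 1,095 in the final data.
- Anyone with later contact, later monitoring documentation, or a 4- or 5-year visit (2.2) has 3 years of follow-up and is unaffected. The simulation makes no allowance for this.
- The SAP gives only the late edge of the window, so every count of early completers is conditional on an assumption.

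A reader might infer that the plan will turn completers into failures and report a wrong tipping point. The document does not support that: the conversion is sequential, completers come last, and under the planning assumptions they are not reached. A reader might also infer that the missing group roughly doubles. That holds only for an assumed symmetric window with about half the visits early.

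**Conclusion.** The three descriptions conflict, and the formal one admits subjects whose 36-month outcome was observed. At the plan's 55% freedom and 10% attrition the tipping point is unchanged; the missing count is inflated by about 37 to 113 over some 67 true exits, on the assumed window and early-visit shares. With better retention or success the definition decides the answer. At 5% per year and 65% freedom the literal rule nearly always reports a tipping point on an observed success, where conversion of every true exit would almost always leave the goal met. Those rates are illustrative and rest on small simulations, but the two sets of runs agree.

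The error understates robustness. It cannot create a false success: the analysis follows a met objective and converts nobody in the primary Kaplan-Meier test. The wording should be corrected before the final analysis, but the success criterion is not in question.

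The 3-year definition also fits the 12-month safety endpoint poorly. A subject who leaves in year 2 or 3 after an event-free 12-month visit counts as missing although the 12-month outcome is known.

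**What to change.** In 3.1.4.2:

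1. Replace the three descriptions with one visit-based definition for effectiveness: CTF-free subjects without a completed 36-month visit. Use it for the trigger, the worst-case branch and steps 1 and 2.
2. In this analysis, set event-free completers of an early 36-month visit to 36 months, mirroring the late-event rule in 3.2.1.3. Exempting them from conversion alone would still leave them outside the risk set at day 1,095.
3. Convert only the subjects defined as missing. If the lower bound stays above 45% after all of them are converted, report that no tipping point exists.
4. For the safety endpoint, define missing by the 12-month visit in the same way.

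The cost is a few sentences in the SAP, plus one filter and one date assignment in the program. No new data are needed.
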